This study examines the effects of aerobic exercise on AD pathophysiology (amyloid burden) and associated "downstream" neurodegeneration (regional atrophy) and cognitive decline in preclinical AD. The proposal extends our ongoing work on the role of exercise to promote a healthier brain and capitalizes on our new status as an AD Center (KU ADC; P30AG035982). We will examine the effects of a 52-week aerobic exercise program in 120 individuals, 70 with preclinical AD and 50 with nonelevated amyloid. We will use existing clinical research infrastructure of the KU ADC to recruit 400 sedentary, cognitively normal (CDR 0) individuals age 65 and older for screening with Florbetapir PET imaging to enroll 70 preclinical AD participants (defined as cognitively normal participants with elevated cerebral amyloid) and 50 individuals with non-elevated cerebral amyloid. Participants will be randomized in a 2:1 ratio to either aerobic exercise or control. Exercise training will occur in a community setting through the network of KUMC approved facilities.

Aim 1: Determine the effect of aerobic exercise on amyloid burden in individuals with preclinical AD (cognitively normal with elevated cerebral amyloid) and those without elevated amyloid. We hypothesize that 52 weeks of aerobic exercise will be associated with lower amyloid burden as measured by Florbetapir PET imaging. Our primary amyloid burden measure will be mean change from baseline to 52 weeks in Florbetapir cortical-to-cerebellar ratio averaged across 6 regions of interest (frontal, temporal, parietal, anterior cingulate, posterior cingulate, and precuneus).

Aim 2: Determine if aerobic exercise attenuates structural brain changes in preclinical AD and those without elevated amyloid. We hypothesize that aerobic exercise will attenuate hippocampal atrophy (1° imaging outcome measure), an area of accelerated atrophy in preclinical AD. Additionally, we will examine the effect of exercise on secondary measures of precuneal and whole-brain atrophy.

Aim 3: Determine the effects of aerobic exercise on cognition in individuals with preclinical AD and those without elevated amyloid. We hypothesize that aerobic exercise will provide cognitive benefits in our primary outcome measure of executive function and in secondary measures of memory and visuospatial function. Additionally, we expect that improvements in memory will correlate with structural preservation in hippocampus.

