This is a randomized controlled trial of 52 weeks of aerobic exercise on sedentary individuals with preclinical AD (n=70) and those with non-elevated cerebral amyloid (n=50) The KU ADC will screen a total of 400 cognitively normal older adults with Florbetapir PET to achieve our enrollment goal. Participants will be randomized in a 2:1 ratio to active aerobic exercise vs. control using randomization sequences generated by the study statistician ([name]). Exercise interventions will be rigorously controlled and supervised in a community-based network of KUMC approved facilities across the Kansas City area. Given our history of 5% drop out over a 6-month exercise trial, we are projecting a 15% annual dropout rate. Participants will have Florbetapir PET and MRI before and after 52 weeks of exercise. Cognitive testing will be completed at baseline, 26-, and 52 weeks. Figure 1 provides an overview of the screening and study events described in more detail below.

Fig. 1 Study Flow and Events

Timeline and Overview of Study Events

Timeline: We anticipate initiating screening of participants within 2 months of funding and beginning enrollment and the intervention within 4 months. Enrollment will be ongoing with screening of 400 participants occurring over three years (~ 3 participants a week) with enrollment completed in the middle of the 4th year of the grant. The final participants will complete the 52-week intervention in the middle of the 5th year, allowing time to complete data analyses and prepare manuscripts.

Screening: The KU ADC will screen a total of 400 participants 65 years of age and older to establish a sufficient cohort (n~120 given an estimated 30% will have evidence of cerebral amyloid) to enroll 70 preclinical AD and 50 amyloid nonelevated participants into the intervention. Screening will include a standard clinical and cognitive evaluation (KU ADC Registry or similar cognitive impairment screening) and Florbetapir PET.

Baseline Evaluation: The baseline evaluation will consist of the following outcome assessments (methodological details provided below) : brain MRI, cognitive testing, physical function assessment (aerobic fitness testing for VO₂ peak, DEXA scan for body composition, and physical function), , physical activity, and phlebotomy.

[figure not shown]
26-Week Evaluation: At 26 weeks (+/- 1 week),, participants will return for an in-person evaluation to repeat cognitive testing and assessments of physical activity.

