Rationale: Magnetic resonance (MR) based volumetric studies are increasingly used as surrogate outcome measures of disease¹²¹ to more efficiently demonstrate an intervention's disease-modifying effect. Our primary focus will be on the effect of exercise in modifying regional atrophy in the hippocampus with secondary outcome measures including rates of whole-brain and precuneal atrophy. The hippocampus is an important structure in mediating memory processes¹²² and is among the earliest affected regions in AD.¹²³ Additionally, atrophy of the hippocampus has been observed in preclinical AD and is associated with asymptomatic cerebral amyloid deposition.^{48, 59} We are also interested in the effect of exercise on regional atrophy in the precuneus, an important node in the default mode network that, along with the hippocampus, appears to be vulnerable to structural and functional decline associated with asymptomatic cerebral amyloidosis.^{61, 124-128} Importantly, these structures may be responsive to exercise: a randomized controlled trial of 52 weeks of exercise attenuated hippocampal atrophy⁷⁷ while physical activity levels are associated with hippocampal and precuneus volumes in nondemented older adults.¹²⁹

Preliminary Experience: Our studies suggest that aerobic fitness (VO_{2peak}) in the earliest stages of AD is associated with whole brain atrophy⁷⁸ and atrophy in the hippocampus⁷⁹ while decline in aerobic fitness over 2 years is associated with greater atrophy in the parahippocampus.⁷⁴ Although our imaging data is limited to aerobic fitness measures (rather than an exercise intervention), the data suggest that exercise to maintain or enhance aerobic fitness may have disease modifying effects on AD-related structural changes. Additionally, our imaging methods are sensitive to hippocampal and precuneus atrophy as we observed annualized rates of atrophy in the hippocampus (1.72% [2.7]) and precuneus (0.56% [0.40]) in nondemented older adults (n=63) over two years. We expect to see greater rates of atrophy in our preclinical AD participants which will enhance our power to observe exercise-related effects.

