CSF and imaging studies indicate that declines in global cognitive ability¹³⁶ and episodic memory (verbal-based,⁵⁰ visuospatial-based,^{137, 138} or both¹³⁹⁻¹⁴¹) are associated with the presence of cerebral amyloid. Thus, secondary outcomes include verbal and visuospatial-based episodic memory measures where we expect decline on these measures will be associated with higher amyloid deposition. Visuospatial ability is an excellent marker of preclinical AD (leading diagnosis by at least 3-years)¹⁴²⁻¹⁴⁵ and was the strongest cognitive indicator for PIB-positive status in a longitudinal study on healthy aging. Visuospatial ability is also strong indicator of executive functioning ability.¹⁴⁶ Although studies of the cognitive effects of aerobic exercise have not resulted in major improvements in episodic memory, no studies have assessed the cognitive effects of exercise in a cohort of individuals with preclinical AD who have expected accelerated rates of decline in episodic memory. By selecting amyloid elevated individuals, we are targeting individuals with preclinical AD who may benefit most from potential disease-modifying effects of aerobic exercise on AD pathophysiology. Thus secondary outcomes include verbal and visuospatial-based episodic memory measures, where we expect decline on these measures will be associated with higher amyloid deposition.

Additionally, three reports indicate cognitive decline in preclinical AD may be mediated by structural changes in the hippocampus^{136, 139, 140} and the concept of preclinical AD posits that hippocampal atrophy is a downstream effect of amyloid deposition. Moreover, this mediation hypothesis may explain a recent finding from Kraemer and colleagues¹⁴⁷ where better visual memory performance was associated with less hippocampal atrophy in exercising nondemented older adults.¹³⁹ Thus, we will test the mediation effect of hippocampal atrophy on the relationship between exercise and cognitive decline over 52-weeks across all 3 outcomes. We anticipate visual memory to be the strongest of the multiple indicators.

Data Acquisition: All participants complete a 2- 3 hour neuropsychological test battery at baseline, 26-weeks, and 52-weeks. This battery includes selected tests with demonstrated responsiveness to aerobic exercise and sensitivity to change in preclinical AD. These tests will be aggregated into several domains: Executive Function, Visual Memory, and Verbal Memory, General Health, Emotional Health.

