A secondary analysis will examine the longitudinal mediation¹⁶³ effect of hippocampal atrophy on the relationship between amyloid binding and cognitive decline (primary and secondary outcomes) over 52-weeks. We anticipate the relationship between exercise and improved cognition will be partially mediated by hippocampal atrophy. Briefly, to evaluate if hippocampal atrophy is a mediator, we will first assess for a positive correlation between cognition with hippocampal volume (i.e., better change in cognition measures associated with less hippocampal atrophy as measured by Pearson’s correlation coefficient, or alternatively, Spearman’s correlation coefficient if a nonparametric approach is required). We will have already evaluated the relationship between exercise and hippocampal changes in Aim 2, anticipating less atrophy in the exercise group. If these bivariate relationships demonstrate associations in these hypothesized directions, we will then model change in cognition as a function of exercise and hippocampal atrophy (simultaneously) using OLS regression. Exercise will be examined both by treatment group assignment and as a continuous measure as described above. The attenuation of the effect of exercise on cognition in these models compared to that from the models without adjustment for hippocampal atrophy, under these additional conditions, would indicate hippocampal atrophy is a mediator of the exercise-cognition relationship. Assessment of the OLS models would follow the approach described in Aim 1 (above).

Sample Size Justification

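### The secondary hippocampal mediation analysis has no amyloid term, so amyloid group, a likely common cause of atrophy and cognitive decline, can mimic a hippocampus-to-cognition link

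*Combined protocol and SAP*

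**What the plan says.** Statistical Analyses for Aim 3 sets out the mediation analysis in steps.

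- First: "we will first assess for a positive correlation between cognition with hippocampal volume", by Pearson's or Spearman's coefficient. The exercise effect on the hippocampus is taken from Aim 2.
- The next step is conditional on direction only: "If these bivariate relationships demonstrate associations in these hypothesized directions".
- Then: "we will then model change in cognition as a function of exercise and hippocampal atrophy (simultaneously) using OLS regression". If the exercise coefficient shrinks relative to the model without atrophy, the hippocampus is called a mediator.

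No covariate or stratum is named here, nor in the analysis text for Aims 1 and 2, where every comparison is between the two treatment arms. That the 70 elevated and 50 non-elevated participants are analysed together is inferred from this; the protocol does not say so in words.

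Elsewhere the protocol describes what it expects of amyloid:

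- Aim 3 Rationale: "the concept of preclinical AD posits that hippocampal atrophy is a downstream effect of amyloid deposition", and the elevated group consists of "individuals with preclinical AD who have expected accelerated rates of decline in episodic memory".
- Aim 2 Preliminary Experience: "We expect to see greater rates of atrophy in our preclinical AD participants".

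Specific Aims, Aim 3, adds the expectation that "improvements in memory will correlate with structural preservation in hippocampus".

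**The concern.** Randomisation protects the total effect of assigned arm on cognition and the effect of arm on the hippocampus. It does not protect the path from hippocampus to cognition, because nobody is assigned to an atrophy rate. Any cause that drives both atrophy and cognitive decline biases that path.

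By the protocol's own expectations, amyloid status is such a cause, and the design mixes the two amyloid groups 70:50. If elevated participants do worse on both measures, the pooled data show a positive hippocampus-cognition association even when none exists within either group. The exception is a chain in which all of amyloid's effect on cognition passes through the hippocampus; amyloid group is then not a confounder.

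At stake are the secondary conclusion that hippocampal preservation carries the cognitive benefit, and the expected memory-hippocampus correlation. Both could appear to be met because of the mix of groups.

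**Working it through.** **Plan's own figure.** The documents give no figure for the mediation analysis. The nearest is Aim 2, the exercise-to-hippocampus path, in Sample Size Justification.

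- Difference in change: (4.98 − 4.89) − (4.83 − 4.90) = 0.16.
- Change SDs at a correlation of 0.95: √(0.74² + 0.69² − 2 × 0.95 × 0.74 × 0.69) = 0.231, and √(2 × 0.80² × 0.05) = 0.253.
- d = 0.16 / √((0.231² + 0.253²)/2) = 0.66, as stated.
- Power with 56 and 28, two-sided 0.05: 81.4% by the normal approximation (80.5% by noncentral t), against 81.4% stated.

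**Inputs for the check.**

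- Completers: 120 × 0.85 = 102, split 2:1 into 68 and 34. The amyloid split is 40 elevated and 28 non-elevated under exercise, 20 and 14 under control.
- Exercise effect on hippocampal change: a = 0.66 SD, from Aim 2.
- Group mix: q = (70/120) × (50/120) = 0.243.
- Assumed, because the documents give no figure: elevated participants do worse by δM SD in hippocampal change and δY SD in cognitive change, in within-group SD units.
- True hippocampus-to-cognition effect: zero.

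**Formula.** Let M = aX − δM·G + e1 and Y = cX − δY·G + e2, where X is arm, G is amyloid group, and e1 and e2 are independent with SD 1. Regressing Y on X and M gives an expected coefficient for M of

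b = q·δM·δY / (1 + q·δM²),

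and the spurious indirect effect is a × b. For a gap of 0.5 SD on both: b = 0.0608 / 1.0608 = 0.057, and 0.66 × 0.057 = 0.038 SD.

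**Results.** The error rate is that of a two-sided 5% test of the atrophy coefficient, by simulation (6,000 to 10,000 trials per setting).

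| δM | δY | b | Spurious indirect effect (SD) | Error, no amyloid term | Error, amyloid group added |
|---|---|---|---|---|---|
| 0.3 | 0.3 | 0.021 | 0.01 | 5–6% | about 5% |
| 0.5 | 0.5 | 0.057 | 0.04 | 9% | about 5% |
| 0.64 | 0.64 | 0.090 | 0.06 | 14–15% | about 5% |
| 0.8 | 0.8 | 0.135 | 0.09 | 27% | about 5% |
| 0.64 | 0.2 | 0.028 | 0.02 | about 6% | about 5% |
| 0.64 | 0.5 | 0.071 | 0.05 | 11% | about 5% |

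**The plan's own rule.** The protocol concludes from attenuation and direction, not from a test of the coefficient. With an assumed direct exercise effect of 0.5 SD on cognition and no mediation, that rule declares mediation in about 50% of trials with no amyloid gap, 71% at 0.5 SD and 81% at 0.64 SD. The 50% is the separate weakness of a rule without a test. The rise above it comes from omitting amyloid group.

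**The case against.** **The contrast may be small.** The non-elevated group is restricted to a mean SUVR of 1.0 or more, about the top third of non-elevated scans, and the protocol thinks it may be enriched with people who accumulate amyloid. The expectation of greater atrophy follows figures from a separate cohort of 63 nondemented adults; it is not stated against this selected group. This stands, and it is why no single gap can be claimed. A reader might take 0.64 SD as documented, since 1.72 / 2.7 = 0.64 from that cohort's annual hippocampal loss and SD. It is not: 1.72% is one cohort's rate of loss, and using it as a gap assumes that elevated participants lose volume at twice that rate.

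**Amyloid is linked mainly to memory.** The Aim 3 Rationale ties amyloid to global ability and episodic memory rather than to executive function, the primary outcome. With a cognitive gap of 0.2 SD or less, the error rate is close to nominal. This stands too: the concern is greatest for the memory outcomes.

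**The spurious effect may be a small share of the exercise effect.** Against the plan's executive effect of d = 2.32, 0.06 SD is 0.06 / 2.32 = 2.6%. Against an assumed effect of 0.5 SD it is 12%. The share depends on an effect not yet known.

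**Amyloid may act through the hippocampus.** The Rationale says that cognitive decline in preclinical AD may be mediated by hippocampal change. If that chain is complete, adjustment is unnecessary and costs some power. The plan does not claim that it is complete. The opening sentence of the mediation paragraph also names amyloid binding as the exposure, while the steps that follow use exercise. That mismatch needs reconciling in its own right.

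**The description is brief.** The plan introduces its steps as a short account and cites a longitudinal mediation method. Even so, the model terms it lists do not include amyloid.

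**Conclusion.** The point holds for this secondary analysis. As written, the hippocampus-to-cognition path is open to confounding by amyloid group, a variable that the trial measures before randomisation and whose effects on both atrophy and memory the protocol anticipates. The size is not known. Under the assumptions above, the bias is negligible at gaps of 0.3 SD on both measures or when the cognitive gap is 0.2 SD or less, and material from about 0.5 SD on both.

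Three stronger readings are not supported.

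- The primary comparisons are not biased: arm is randomised, and omitting amyloid group from a comparison of arms introduces no bias.
- It does not follow that a mediation finding would be false, only that the planned analysis could not separate mediation from the mix of groups.
- Age is not shown to be a second confounder. The protocol speaks of age-related decline in brain and cognition, but gives no figure for age and one-year change, and stable age differences in level cancel in change scores.

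Severity is minor to moderate.

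**What to change.** In the mediation paragraph of Statistical Analyses for Aim 3:

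1. Add baseline amyloid group, as determined by the screening scan, to both the exercise-only and the exercise-plus-atrophy OLS models. It is fixed before randomisation, so adjusting for it cannot remove part of an exercise effect.
2. Replace the raw correlation of cognitive change with hippocampal change by one that is partial on amyloid group.
3. Base statements about mediation on these adjusted results. Report the Aim 3 memory-hippocampus correlation both unadjusted and adjusted, since the two answer different questions.

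Age may be prespecified as a further baseline covariate as a precaution. Baseline hippocampal volume and baseline cognition are optional and not needed for this point. Adjustment for amyloid group removes this one shared cause; others may remain.

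The cost is a sentence in the plan and no new data. If amyloid acts on cognition only through the hippocampus, power for a true atrophy slope of 0.3 falls by about 3 points: from 86% to 83% with a hippocampal gap of 0.5 SD, and from 87% to 84% with 0.64 SD.

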We have identified primary endpoints for intent-to-treat analyses between treatment groups within each study aim: change in amyloid burden (Aim 1); hippocampal atrophy (Aim 2); and change in executive function (Aim 3). Other endpoints and analyses will be described in resulting publications as secondary. For all analyses the traditional type I error rate of $\alpha=0.05$ will be used. We will use two-sided tests to further protect against spurious results. Our primary intent-to-treat analyses will be based on the two-sample t-test. **Table 2** presents the power for each aim of our study corresponding to our primary measures. Anticipated effect sizes are presented using Cohen’s d (expected average group difference divided by the assumed, common standard deviation). We assumed 15% of our 100 enrolled subjects will be lost to attrition, so power calculations assumed 56 subjects in our exercise intervention arm and 28 subjects in our control group.

Table 2. Anticipated study power

Study aim	Primary measure*	Effect size (Cohen’s d)	Power
Aim 1	Amyloid burden	0.79	92.9%
Aim 2	Hippocampal volume	0.66	81.4%
Aim 3	Executive function	2.32	>95%

*Primary measures are change from baseline to 52-week follow-up.

Aim 1: A 78 week study assessing Bapineuzumab¹¹⁹ in AD demonstrated a mean change in cortical PIB retention (average across six cortical regions) of -0.09 (0.16 SD) for those treated with Bapineuzumab (n=20) and 0.20 (0.09) for those on placebo (n=7). Given the differences in our proposed study (preclinical AD sample, lower expected amyloid burden, shorter duration) we determined power allowing exercise to have a lower effect size. An effect size only 40% as large will produce a Cohen’s d of 0.79. Thus, Aim 1 will have 93% power to detect this conservative anticipated effect of exercise on amyloid burden (and 81.9% power to detect 30% of the Bapineuzumab effect size).

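### The 81.9% power stated for 30% of the Bapineuzumab effect does not reproduce; on the plan's own inputs it is about 72%

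*Combined protocol and SAP*

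**What the plan says.** All the inputs stand in the Sample Size Justification section of the combined protocol and SAP.

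- **Error rate and test:** the type I error rate is 0.05 and the primary comparison is a two-sample t-test. On sidedness the plan says "We will use two-sided tests to further protect against spurious results".
- **Numbers analysed:** the section starts from 100 enrolled and removes 15% for dropout. It states that "power calculations assumed 56 subjects in our exercise intervention arm and 28 subjects in our control group".
- **Source of the Aim 1 effect:** a 78-week Bapineuzumab trial, which the plan reports "demonstrated a mean change in cortical PIB retention (average across six cortical regions) of -0.09 (0.16 SD) for those treated with Bapineuzumab (n=20"). The placebo arm (n = 7) changed by 0.20 (SD 0.09).
- **Planning effect:** the plan takes 40% of that effect and puts it at d = 0.79. Table 2 gives 92.9% power for this.
- **Smaller effect:** the same sentence that reports 93% adds, in parentheses, "and 81.9% power to detect 30% of the Bapineuzumab effect size".

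No different sample size, test or sidedness is given for the last figure.

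**The concern.** The two power figures in one sentence are meant to differ only in effect size, 40% against 30% of the same reference effect. Cutting the effect by a quarter lowers power more than the plan reports, so either an input changed without being stated or the second figure is wrong.

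The figure matters because the effect is borrowed from an antibody trial in AD. The plan itself says its own setting differs: a preclinical sample, lower expected amyloid burden and a shorter duration. A smaller effect than the planning value is therefore the case a reader most wants to see, and this parenthesis is the only place where the plan shows it for Aim 1. The paragraph on 2:1 randomisation then relies on power being sufficient for the primary endpoints when it accepts the loss from unequal allocation.

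**Working it through.** **Step 1. Full reference effect.**

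Pooled SD = √[(19 × 0.16² + 6 × 0.09²) / 25] = 0.1463.

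Difference in mean change = 0.20 − (−0.09) = 0.29.

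d = 0.29 / 0.1463 = 1.982.

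**Step 2. Reproduce the plan's figures, to fix the method.**

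The noncentrality parameter is d × √(n₁n₂ / (n₁ + n₂)). With 56 and 28, the multiplier is √(56 × 28 / 84) = 4.320.

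- *Aim 1, 40% of the effect:* d = 0.4 × 1.982 = 0.793, the stated 0.79. Noncentrality = 3.426. Two-sided power by normal approximation = Φ(3.426 − 1.960) = 92.9%, as stated. By noncentral t (82 df) it is 92.3%.
- *Aim 2, d = 0.66:* noncentrality = 2.852. Φ(2.852 − 1.960) = 81.4%, as stated. By noncentral t it is 80.5%.

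So the pooled SD, the 56:28 split, two-sided 0.05 and the normal approximation account for both of these Table 2 figures.

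**Step 3. The 30% figure on the same inputs.**

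d = 0.3 × 1.982 = 0.595. Noncentrality = 0.595 × 4.320 = 2.57.

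- Normal approximation: Φ(2.569 − 1.960) = 72.9%.
- Noncentral t, 82 df: 71.9%.

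Starting from the rounded 0.79 instead (0.79 × 0.3 / 0.4 = 0.5925) gives 72.6% and 71.6%. The stated figure is 81.9%.

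**Step 4. Effect that would give 81.9%.** At 56:28, two-sided, it needs d = 0.665 (normal) to 0.673 (t). That is 33.5% to 33.9% of 1.982, not 30%.

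**Step 5. Other readings.** A valid explanation must give 81.9% at 30% and also 92.9% at 40%, with d = 0.79.

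| Reading | Power at 30% | Result at 40% |
|---|---|---|
| Two-sided, 56:28, pooled SD | 71.9% (t), 72.9% (normal) | 92.3% (t), 92.9% (normal): matches |
| One-sided 0.05, 56:28 | 81.7% (t), 82.2% (normal) | about 96% |
| Unweighted mean of the two variances (SD 0.130) | 81.6% (t), 82.5% (normal) | d = 0.89, not 0.79 |
| 1:1 allocation, 42:42 | 76.8% (t), 77.8% (normal) | about 95% |
| No attrition from 100, 67:33 | 79.1% (t), 79.9% (normal) | about 96% |
| 120 enrolled less 15%, 68:34 | 80.1% (t), 80.8% (normal) | about 96% |

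None of these readings gives both figures. The one-sided reading fits the 30% figure closely and may be where it came from, as may a one-digit slip from 71.9%; the documents do not settle which.

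**The case against.** The arithmetic is not in dispute. The case on the other side is about consequence.

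First, the planning effect is 40%, its 92.9% reproduces, and nothing shows that the 30% remark set the sample size. No endpoint, analysis or decision rule depends on it, and the plan names no 80% threshold that the remark has to clear. This stands: the error is confined to one sensitivity figure.

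Second, the current version enrols 120, and the Aim 1 test compares the arms without restriction by amyloid status. With 15% loss, 120 × 0.85 = 102, or 68:34, and power at 30% is about 80%, close to the printed figure. This is a fair point about the trial as now designed, but it does not rescue the statement. The section still assumes 100 enrolled and 84 analysed, and 68:34 would put the neighbouring figure at about 96%. It also requires the exercise effect to be as large in non-elevated participants as in those with preclinical AD, which the plan does not argue.

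Third, the plan's own figures come from the normal approximation, so a like-for-like correction is 73%. That is right as a matter of consistency. The planned test is a t-test, for which 72% is the exact value. Either serves if the method is named and used for both figures in the sentence.

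**Conclusion.** The 81.9% is wrong as written. On the plan's stated inputs, power to detect 30% of the Bapineuzumab effect is 71.9% by noncentral t or 72.9% by the normal approximation. The overstatement is 9 to 10 points, well beyond rounding. The risk of missing such an effect is about 28% (27% by the normal approximation), against the 18% that the printed figure implies.

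This rests only on inputs the plan states: the reference trial's means, SDs and group sizes, 56:28 analysed, and two-sided 0.05. Pooling by degrees of freedom is not stated but is confirmed by the printed d of 0.79. The headline Aim 1 power of 92.9% is not affected.

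Two figures put the result in context for the current enrolment, and both rest on assumptions. With 68:34 completers and an equal effect in all participants, power at 30% is 80.1%. In the preclinical AD group alone, 70 × 0.85 ≈ 60, or 40:20 if that group also splits 2:1, it is 57.0%. Both are by noncentral t.

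**What to change.** In the Aim 1 paragraph of the Sample Size Justification, change 81.9% to 72% for 56:28 at two-sided 0.05, and say that it is the t-test value. For consistency, either give the 40% figure by the same method (92.3%) or keep 92.9% and write 73% by the normal approximation.

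When Table 2 is recomputed for 120 enrolled, restate this sentence with it: about 80% at 68:34, with the equal-effect assumption written out, and 57% for the preclinical AD group alone.

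The cost is one corrected number and a short note on method. No design or analysis change follows, but the figure is less favourable than the one now printed.
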